#### 9.0 BIOSTATISTICAL CONSIDERATIONS

**Phase I:** Because this is the pilot phase, in which the primary purpose is to examine the feasibility and acceptability of the intervention and not to test a hypothesis, we have not performed a power analysis to determine the required sample size for this phase. Instead our primary goal was to evaluate the feasibility and acceptability of the program. 

Phase II, Aim 1 (Implementation-Effectiveness Trial): We will test our hypotheses using a two-arm cluster randomized control trial. Participating clinics will be randomized into two groups: Intervention and Usual Care. Randomization will be stratified on health system. Our study design aligns with the core principles of the PRECIS-2 framework. Our eligibility criteria are broad and consistent with the realities of rural primary care (e.g., small sample sizes, limited quality improvement capacity). Our patient recruitment approach for the direct mail and navigation programs is aligned with routine care and standard quality improvement approaches and requires no individual consent. Participating clinics will serve populations that display CRC screening disparities, and be diverse in terms of EHR, rural geographic locations, and populations served. Our intervention is flexible and is designed to be adapted according to payer and clinics' resources and preferences. Our primary outcome, completion of any CRC screening, is pragmatic and relevant to patients, clinics, and payers (CCOs), and our primary analysis follows the intention-to-treat concept. We will collect data 6 times from the CCOs. Data will be transferred every 6 months from the Spring of 2021 to the Fall of 2023 to be able to capture up to 18 months of follow-up following each mailing.

The primary effectiveness outcome of this study at the patient level is the completion of any colorectal cancer (CRC) screening (for study-eligible patients). Consistent with the pragmatic nature of the trial, we will use claims, vendor data, and EHR data for calculating CRC screening outcomes. Comparing the likelihood of receiving CRC screening between intervention and usual care groups at 6-month post participant list-pull date, we hypothesize that CRC screening will be more likely in patients allocated to the intervention group versus the usual care group. To examine the effectiveness of the program CRC screening completion at 6 months, we will use the generalized form of the hierarchical linear model (HLM; using a logit link and binomial distribution, aka multilevel logistic regression) to account for the clustering of patients within clinics and the assignment to arm at the clinic level. The variables that will be included in the model are the clinic baseline screening rate (if available) and a binary indicator of arm (1=tailored, 0=standard) as fixed effects and clinic is a random effect. A positive and significant coefficient for arm would provide support for the effectiveness of the intervention. We will do a moderator analysis at all levels to explore the impact of patient and clinics characteristics (see outcomes table above), and implementation components affecting outreach on completion likelihood in groups of patients determined at analysis (e.g. never screened, Hispanic, etc.).

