In Phase II (Years 02-05), we will test our intervention using a two-arm cluster randomized control trial in 30 rural primary care clinics using program training and practice facilitation to support implementation. Participating clinics will be randomized into two groups: Intervention and Usual Care. Randomization will be stratified on health system. As in the pilot, the intervention combines: (1) a clinic-health planvendor supported direct-mail fecal testing program with targeted outreach for patients who have never been screened or who have yet to establish care and (2) patient navigation for those who are referred for colonoscopy as either the primary screening or for follow-up from an abnormal fecal test. We will evaluate effectiveness, implementation, and maintenance of the intervention through quantitative and qualitative measures. Results from the trial will inform scale-up of the program through partnerships with 20 regional and national organizations that serve rural/frontier primary care clinics using webinars, train-the-trainer workshops and collaborative learning activities.

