Patient interviews: We will conduct one-on-one interviews with patients who receive the direct mail and patient navigation programs. Interviews will explore patient experiences with the program, including reaction, acceptability, satisfaction, and perceptions of usefulness; facilitators of, and barriers to, participating in the program and obtaining a follow-up colonoscopy; unintended consequences; and suggestions for improvement

Interviews and surveys with regional and organizational partners: To assess perceptions of the intervention and its impact on the broader community, we will interview CCO leaders, endoscopy providers (e.g., GI specialists, general surgeons, primary care clinicians) who treated study participants, and community organizations, including transportation service providers. Up to three interviews will occur throughout the duration of the study, including at baseline (pre-implementation), at the mid-point (approximately 12 months after the first-year implementation start), and post-implementation (approximately 12 months after the second-year implementation start). To evaluate the impact of scale-up activities we will conduct interviews and brief evaluation surveys with organizational leaders who participate in the trainings.

Patient outcomes data and patient navigation registry (Evaluation): Direct mail outreach and patient navigation activities will be tracked using reports from direct mail vendors, claims data from participating Medicaid health plans, clinic data from the electronic health record, chart abstraction data conducted by ORPRN or clinic staff, and data on navigation from a REDCap database. The mailed FIT and patient navigation interventions will be delivered by clinic and health plan staff as part of standard care. Clinics will be randomized to implement the interventions in different years to provide comparison groups. Claims data will be sent to the research team at OHSU from the participating payers based on their data pull of patients eligible for CRC screening in the clinics randomized to implement the intervention. Vendor reports will be sent to the CCO and research team based at OHSU. A clinic-level chart audit will be used to evaluate CRC screening and follow-up colonoscopy for patients with an abnormal FIT in intervention and control clinics.

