Data for this project (i.e., process and survey data elements and patient navigation outcomes (such as number of patients who received patient navigation, number of patients with missed / canceled appointments or inadequate bowel preparation), will be stored in OCTRI's installation of REDCap, a highly secure and robust web-based research data collection and management system.

Features of REDCap that protect participants' privacy and data security include:

[figure not shown]
• Physical Security: OCTRI's REDCap software is housed on servers located in ITG's Advanced Computing Center providing locked physical security

- Electronic Security: The REDCap servers are housed behind both the OHSU firewall and a second ACC firewall. All transmissions of data from the application are encrypted over HTTPS with the industry standard TLS 1.1 protocol (AES 256-bit encryption).
- Controlled User Access: REDCap employs a robust multi-level security system that enables researchers to easily implement "minimum necessary" data access for their research staff, including specification of data fields that are identifiers. This feature includes "single click" ability to provide completely deidentified (removing all identified data fields and shifting dates) for analysis or other purposes. User activities are logged to enable auditing of all data access. Access is integrated with OHSU's network such that users who are also OHSU employees are authenticated against their OHSU network credentials.
- Data Integrity: REDCap is jointly managed in accordance with OHSU Information Security Directives by ACC staff and members of OCTRI's Biomedical Informatics Program, ensuring fidelity of database configuration and back-ups. User activities are logged to enable auditing of all data changes.

Data from the vendor and REDCap database will be merged with claims data to generate evaluation reports. To avoid bias in colonoscopy capture across baseline and follow-up time-points, ORPRN practice facilitators will perform a chart audit on all patients who were eligible for the direct mail program. The chart audit will confirm FIT completion and monitor for colonoscopy referral and receipt, pathology results, and referral to care (i.e. surveillance or cancer treatment), as indicated.

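### Does counting vendor data towards the primary outcome tilt the 6-month comparison in favour of the intervention arm?

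*Combined protocol and SAP*

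**What the plan says.** Section 9.0 compares intervention with usual care on completion of any screening, 6 months after the participant list is pulled. On data sources it states "we will use claims, vendor data, and EHR data for calculating CRC screening outcomes". The effectiveness row of the aims table in Section 8.0 gives a longer list that adds administrative, laboratory and survey data. Neither place says how the sources are combined or what happens when they disagree.

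On the vendor, the Abstract says "the intervention combines: (1) a clinic-health planvendor supported direct-mail fecal testing program", and Section 7.0 says "Direct mail outreach and patient navigation activities will be tracked using reports from direct mail vendors". Section 7.0 also says "Data from the vendor and REDCap database will be merged with claims data to generate evaluation reports".

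On claims, Section 7.0 describes the payers' "data pull of patients eligible for CRC screening in the clinics randomized to implement the intervention". Section 9.0 says "We will collect data 6 times from the CCOs" and sets no limit to one arm.

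On charts, Section 7.0 says that a clinic-level "chart audit will be used to evaluate CRC screening and follow-up colonoscopy for patients with an abnormal FIT in intervention and control clinics", and later: "The chart audit will confirm FIT completion and monitor for colonoscopy referral and receipt". Section 10.2 (Informed Consent) describes chart review for all participants eligible for screening.

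**The concern.** In a trial of an outreach programme, a data source generated by the programme can detect events in one arm only. If a mailed kit that only the vendor recorded counts as a screen, and a usual-care patient has no comparable route to being counted, part of the observed difference could reflect better detection rather than more screening. Section 9.0 names the vendor source for the primary endpoint, gives no combining rule and plans no analysis restricted to sources found in both arms. The claims sentence in Section 7.0 adds to the worry, because on its own it can be read as a data pull for intervention clinics only. At stake would be the credibility of the primary effect estimate: a reader could not tell how much of it rested on the one-arm source.

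**Working it through.** The plan states no Phase II power, screening rate, intracluster correlation (ICC) or capture rate, so there is no figure of its own to reproduce. The check has three parts.

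**1. Is there a source that covers both arms?** Three statements, read together:

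- Section 7.0 places the chart audit in intervention and control clinics and uses it to evaluate screening. The phrase about an abnormal FIT most naturally attaches to follow-up colonoscopy. A patient with an abnormal FIT has already been screened, so auditing screening in those patients alone would be empty.
- Section 7.0 has the audit confirm FIT completion for everyone eligible for the mailing programme.
- Section 10.2 extends chart review to all screening-eligible participants.

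EHR data are among the sources that Section 9.0 names. A both-arm source that captures FITs is therefore already planned.

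**2. Are claims pulled for one arm only?** The sentence shortly before the claims wording says that clinics are randomized to implement in different years. On that reading every randomized clinic is one that implements, and the pull covers all of them. A one-arm pull would also leave the comparison in Section 9.0 without control-arm claims. The reference to follow-up after each mailing belongs to the transfer schedule. Transfers every 6 months from Spring 2021 to Fall 2023 make six, and Fall 2023 is 18 months after the Spring 2022 second-year start. The endpoint window is defined separately, from list pull, in both groups.

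**3. How much could vendor-only tests matter?** Inputs: 3,960 patients and 30 clinics (aims table, Section 8.0), or 4,500 patients (Abstract). Assumed: equal arms, v vendor-only tests, and p = proportion screened in each arm before those tests are added.

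- Per arm: 3,960/2 = 1,980 patients and 15 clinics.
- Shift in the arm difference = v/1,980. For v = 10, 20 and 40 this is 0.5, 1.0 and 2.0 points. Twenty tests are 20/15 = 1.3 per intervention clinic.
- With 4,500 patients: 2,250 per arm, so 22.5 tests equal 1 point.
- Crude odds ratio = [q/(1−q)]/[p/(1−p)], with q = p + v/1,980. At p = 15%: 1.04, 1.08 and 1.16 for v = 10, 20 and 40. At v = 20: 1.11 if p = 10% and 1.06 if p = 25%.

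A harsher illustration assumes no true effect. Let common sources capture a share s of completed screens, and let vendor reports recover a share f of the rest in the intervention arm only. Observed rates are then p·s in usual care and p·[s + (1−s)·f] in the intervention arm, where p is now the true rate. With p = 20%, s = 90% and f = 100%, they are 18% and 20%. The gap is 2.0 points (odds ratio 1.14), which is 0.02 × 1,980 = 39.6 vendor-only tests. With 132 patients per clinic the design effect is 1 + 131·ICC, or 2.31, 4.93 and 7.55 for ICC 0.01, 0.03 and 0.05. A two-sided 5% test then rejects in 18%, 11% and 9% of trials. At s = 95% the gap is 1.0 point and rejection is 8%, 7% and 6%.

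These results depend wholly on s and f, and f = 100% is an extreme value: a mail vendor can see its own kits but not a colonoscopy or a kit handed out in clinic. If the audit is complete, s approaches 100% and the gap goes to 0.

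**The case for a change.** The best case for a change is that Section 9.0 never mentions the audit and never says that EHR data means audit data. Section 7.0 gives the audit's purpose as avoiding bias across time-points, not across arms, and defines its scope by eligibility for the mailing programme. The two source lists differ. If capture from the common sources were poor, the illustration shows that error rates could rise well above 5%. The proposed remedy costs only a few sentences and one more model fit.

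Part of this stands. The combining rule is not written down, the audit's scope could be worded more tightly, and it is a fair inference, though nowhere stated, that usual-care clinics have no vendor data in the comparison period. What does not follow is that the plan as written gives a wrong answer. The outcome is completion of any screening, so the natural rule is that a completed test inside the window counts whichever record shows it. The audit scope in Sections 7.0 and 10.2 belongs to the same document and need not be repeated in Section 9.0.

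The extra analysis would also be hard to interpret. A vendor-only test may be a real screen that claims and charts missed. Dropping 20 such tests would understate a true difference by the same 1.0 point. A smaller restricted estimate could therefore mean detection bias or lost genuine kits, and the analysis cannot separate the two.

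**Conclusion.** The concern does not call for a change. Followed as written, the plan reviews charts in both arms and verifies FIT completion, so ascertainment is largely equal. Any effect of vendor data is confined to tests that claims and the chart audit both miss. Each 20 of these would be worth 1.0 point, assuming 1,980 patients per arm. Nothing in the documents suggests how many there would be, and the number may be zero. The direction of any error is also open, since counting such tests may correct under-capture of mailed kits. The combining rule is a gap that analysts would fill sensibly, the claims sentence is loose wording that its context resolves, and a restricted refit would not alter the primary result. This conclusion rests on the audit being carried out for all screening-eligible patients in both arms, as Sections 7.0 and 10.2 describe.

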#### 4.0 STUDY POPULATION

The study team will recruit eligible CCOs and rural clinics, and we will work in turn with clinics to engage providers, staff, and patients. Our eligibility criteria for CCOs, clinics, clinics staff, patients and organizational partners are below.

CCOs/CCO staff: 1) serving a majority of counties that are predominantly rural based on 2010 RUCA Codes (Codes 4-10); 2) willing to participate in data collection activities (e.g., producing claims data, interviews).

Clinics: 1) Clinics will be eligible for the cluster randomization if there are 30 or more patients eligible for screening, 2) are classified as rural according to RUCA (Codes 4-10) or Oregon Office of Rural Health designations, 3) are served by CCOs agreeing to participate in the project; and 4) willing to implement the intervention into their clinic for the study.

Clinic Staff/Providers: 1) employed as a clinician or ancillary staff member in a participating clinic; 2) willing to participate in data collection activities (e.g., interviews, observation, surveys).

Patients: 1) attributed to participating clinic; and 2) are enrolled in Medicaid or Dual eligible; 3) eligible for CRC screening;

a. For the subset of patients that will be invited to participate in key informant interviews, a 5th eligibility criteria is consent to participate.

Exclusion criteria: Clinics are excluded if they have current or ongoing participating in other mailed fecal testing research projects in the Medicaid population. Patients are excluded if they are current for screening, have comorbid conditions that make patients poor candidates for screening based on clinical judgment (e.g., end-stage renal disease, enrollment in hospice), are not an established patient or for other reasons documented by the clinics.

Community or regional/organizational partners (includes endoscopy providers, community-based outreach workers, or leaders from regional or national organizations who participate in the pilot, pragmatic trial, or scale-up study) 1) involved in study activities (training, care delivery); 2) willing to participate in data collection activities (e.g., trainings, interviews, surveys).

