# 7.0 STUDY PROCEDURES AND SCHEDULE OF EVENTS

CCO interview, readiness assessment, and survey: CCOs that express interest in participating in the trial will be invited to participate in a semi-structured interview (in-person or via phone) and complete a baseline survey to confirm CCO characteristics (e.g., size, number of primary care clinics in rural/frontier counties) as well as information about CCO data infrastructure, relationships with clinics, and quality improvement capacity. Readiness questions will be drawn from the literature and explore the CCO's prior experience with payment and quality improvement initiatives related to CRC screening and follow-up care.

Clinic survey, readiness assessment, observation and interviews: For clinics expressing interest in the trial, we will conduct semi-structured interviews (in-person or via phone) with clinic leadership to assess clinic characteristics, capacity and readiness to adopt the program and participate in the trial. Clinic characteristics will include descriptive data (e.g., ownership, primary care clinician number and FTE, EHR vendor and version), baseline CRC screening rates and if the clinic currently utilizes audit and

feedback, and details on current workflows related to CRC screening and follow-up (including provider CRC screening modality preferences). Capacity questions will explore general capacity as well as specific capacity related to CRC screening. Readiness questions will draw on prior work by Weiner, Hannon, and others, and utilize a clinic-level readiness survey piloted by our team during [name] K07.

We will conduct clinic surveys, interviews, and observations with clinic staff in various roles related to the program (e.g., outreach workers, patient navigators, quality improvement leads) to assess clinic/health system level factors that may influence outcomes. These assessments will happen at baseline and after implementation of the pilot as well as for each arm of the trial (post-implementation at 6-9 months as well as implementation context, maintenance, and sustainability approximately 12 months later [i.e., clinic exit interviews]).

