recruit clinics; conduct	exclusion criteria for CCOs and clinic	literature,	board on inclusion and exclusion	2020		
baseline assessment; use	participation in Phase II.	statistical power	criteria			
results from pilot to		requirements				
prepare to conduct a	b. Develop CCO and clinic	Relevant	Feedback from local advisory	Jan – Mar		
large-scale, pragmatic	recruitment materials	literature	board	2020		
implementation-	b. Successfully engage 3 CCOs and 30	Feasibility data	List of participating CCOs and	Mar – Sep		
effectiveness trial and	rural/frontier clinics for the main trial	from pilot study	selected clinic characteristics	2020		
scale-up (see Phase II).	d. Develop manual outlining trial	Feasibility data	Feedback from advisory board on	Apr – Sep		
	protocols (including quality assurance	from pilot study	recruitment materials; study	2020		
	protocols), scopes of work, and		protocol; scope of work			
	associated budgets.					

Aims	Assessment/	Data Sources	Description	Timeline
	Measurement			
Aim 1. Conduct a large-scale pragmatic study, cluster randomized control trial, to assess the implementation, effectiveness, and maintenance of the program piloted in Phase I in 30 rural primary care clinics (n ~ 3,960 patients aged 45 – 75) using practice facilitation to support implementation. Using a mixed methods approach, identify patient-, clinic/health system-, and payer/policy/community-level factors that are associated with reach, effectiveness, implementation and maintenance	Assessment of effectiveness (patient and clinic level).	Administrative data, claims data, EHR data from clinics, vendor data, laboratory data, survey data.	Patient Level Outcome (Primary): Completion of any CRC screening Clinic Level Outcome: Proportion of Medicaid patients screened for CRC We will compare the intervention vs. control clinics after adjusting for baseline at 6 and 12 months. The primary endpoint is 6 months. Secondary outcomes: completion of testing types (fecal testing, FIT-DNA, CT Colonography, Colonoscopy, Flex Sigmoidoscopy; patient level) and % completion (clinic level); time to screening from study-eligible patient list pull (patient level); FIT results (patient level); follow-up colonoscopy completion (patient level); time to colonoscopy from abnormal FIT result (patient level); and adenomas or cancers detected (patient level).	2021-Sep 2024

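### Clinics are randomized within health-system strata, but the primary model has no health-system term and the plan does not say why

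*Combined protocol and SAP*

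**What the plan says.** Sections 1.0 and 9.0 make the same statement about the design: "Randomization will be stratified on health system". The units randomized are about 30 clinics.

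Section 9.0 then specifies the primary analysis as a multilevel logistic regression of any CRC screening by 6 months. Its terms are given as a list: "The variables that will be included in the model are the clinic baseline screening rate (if available) and a binary indicator of arm", entered "as fixed effects and clinic is a random effect". The conclusion about effectiveness rests on the arm coefficient from that model. The stated purpose of the model is to handle clustering within clinics and clinic-level assignment; stratification is not mentioned.

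Three other places bear on the point:

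- Section 8.0 (Phase II, Aim 1) adds only baseline adjustment: "We will compare the intervention vs. control clinics after adjusting for baseline at 6 and 12 months".
- Section 8.0 also plans to "identify patient-, clinic/health system-, and payer/policy/community-level factors that are associated with reach, effectiveness, implementation and maintenance", and section 9.0 plans exploratory moderator analyses. Neither puts the strata into the primary test.
- Section 7.0 collects the covariate ("Clinic characteristics will include descriptive data (e.g., ownership, primary care clinician number and FTE, EHR vendor and version), baseline CRC screening rates") and plans clinic surveys and interviews "to assess clinic/health system level factors that may influence outcomes". It does not report that systems do differ.

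No section says how many health systems there are, what counts as one, or why the stratification factor is left out of the primary model.

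**The concern.** When arms are balanced within systems, differences between systems largely cancel out of the arm comparison. A model with no system term does not know this. It assigns those differences to the clinic random effect and so reports a standard error for arm that is larger than the estimate's real variability. The estimate is not biased and, with a calibrated test, false positives do not rise. What is lost is efficiency: the test becomes conservative to the extent that systems differ.

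This matters because information is limited by the number of clinics, not by the number of patients. With about 30 clinics there is little precision to give away. The opposite risk is also real: if systems hardly differ, or are many and small, one fixed term per system can cost power. The choice therefore needs to be made in the plan.

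**Working it through.** **1. Is there a planned figure to reproduce?** No. The documents give no Phase II power calculation, ICC, control rate, effect size or number of systems. The first step is the textual comparison above: health system is in the randomization and is absent from the model as a fixed effect, a random effect or a stratified test.

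**2. Direction of the error.** One simulation without a baseline covariate isolates the mechanism. Inputs: 30 clinics (section 9.0 with section 8.0); 3,960/30 = 132 patients per clinic (section 8.0). Assumed: 20% control rate, within-system clinic SD 0.3 on the logit scale, three systems of ten, between-system SD 0.3, so the system share is 0.09/(0.09 + 0.09) = 50%. Results:

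- mean reported standard error without the system term: 0.162
- mean reported standard error with it: 0.135
- actual SD of the estimate: 0.139

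The planned form overstates the standard error by 0.162/0.139 = 1.17, or about 17%. This shows direction only. With no baseline covariate and a large assumed share, its power figures should not be carried over.

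**3. Size, with the baseline covariate.** Assumed: 15% control rate, odds ratio 1.6, ICC 0.05, baseline correlation 0.6, 132 patients per clinic, clinic-level empirical-logit regression with a t reference. Three separately coded simulations, three to six systems, 30-50% system share:

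| Run | Type I error without term | With fixed term | Power change (points) |
|---|---|---|---|
| A (20,000 trials per cell) | 2.8-3.9% | 4.7-5.2% | +2.2 to +5.5 |
| B (5,000 trials per cell) | 3.2-4.1% | 4.9-5.5% | +2.0 to +4.3 |
| C | 3.4-4.7% | 4.6-5.5% | +1.2 to +4.2 |

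Sensitivity in run A, three to six systems:

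- At 10% share the power change is -0.9 to +0.8 points.
- If baseline rates track systems closely (system-level correlation 0.9), the change is -1.5 to +0.2 points at 10% share and +0.3 to +1.4 at 30%.
- With unequal clinic sizes (section 4.0: "Clinics will be eligible for the cluster randomization if there are 30 or more patients eligible for screening"; coefficient of variation 0.65 assumed), it is -1.1 to +0.8 at 10% and +2.2 to +5.8 at 30-50%.

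**4. Cost of fixed terms if systems do not differ.** This can be checked by hand. The information on arm is I = sum over systems of n1 x n0/n, where n1 and n0 are a system's clinics by arm. Without strata, 15 against 15 gives 15 x 15/30 = 7.5 on 30 - 3 = 27 df (t = 2.052). With S fixed systems the df are 30 - S - 2. Relative interval width = sqrt(7.5/I) x t(30 - S - 2)/2.052.

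| System sizes | I | df | t | Relative width | Simulated power change at 0% share |
|---|---|---|---|---|---|
| 3 x 10 | 7.5 | 25 | 2.060 | 1.004 | -0.8 |
| 6 x 5 | 6 x 6/5 = 7.2 | 22 | 2.074 | 1.032 | -2.9 |
| 18/8/2/1/1 | 4.5 + 2 + 0.5 + 0 + 0 = 7.0 | 23 | 2.069 | 1.044 | -2.9 to -3.4 |
| 26/1/1/1/1 | 13 x 13/26 = 6.5 | 23 | 2.069 | 1.083 | -6.2 to -6.8 |
| 10 x 3 | 10 x 2/3 = 6.67 | 18 | 2.101 | 1.086 | -6.0 to -7.4 |

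The 3 x 10 and 6 x 5 power figures are from REML-type multilevel logistic runs; clinic-level runs over layouts of three to six systems gave -0.3 to -2.4. The hand widths agree with the simulated ones (0.5-3.4% wider for three to six systems, 9% for ten). A single-clinic system with its own fixed effect contributes nothing to the arm estimate.

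The share at which fixed terms break even was about 2% (3 x 10), 16% (6 x 5) and 34% (10 x 3).

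**5. Random system effect.** Across the layouts in run A (3 x 10, 5 x 6, 6 x 5, 12/8/5/3/2 and 10 x 3), power changed by +0.3 to +0.7 points at 0% share and +4.3 to +6.1 at 50%. Type I error was 4.7-6.0% over the clinic-level and multilevel logistic runs.

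**6. Estimation method.** With plain maximum likelihood and a Wald z test, type I error was 4.9-8.1% for the planned model and 8.0-14.6% once fixed strata were added. The term should not be added without a small-sample method.

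**The case against.** The strongest case against acting has four parts.

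*The consequence depends on an estimator that the plan does not name.* This stands. The planned model is conservative only under a calibrated test; under maximum likelihood with Wald z it is not. That is why the term and the small-sample method must be specified together.

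*The harm is unknown in sign.* This also stands. Every driver in the illustration is assumed, and at low system shares a fixed term gains nothing or loses a little. A reader might infer that the primary test is biased, invalid or certain to lose power; the documents support none of these.

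*Baseline adjustment already does much of the work.* In part. When baseline rates track systems closely, most of the gain disappears. But section 9.0 includes that covariate only where it is available, and it does not stand in for the stratification factor.

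*The random effect is not a free remedy.* Agreed. Its apparent gains compare tests of unequal size, since its type I error reached 6.0%.

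Two tempting inferences should also be resisted. Because section 8.0 lists health system separately from payer, a reader might conclude that the three CCOs cannot be the strata. That list names levels of factors to study and does not define the stratum. Usage elsewhere is loose: section 1.0 has health-system or clinic staff delivering the program, section 7.0 clinic and health-plan staff. The documents neither establish nor exclude CCOs as strata.

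A reader might also want a simple rule based on the average number of clinics per system. The 18/8/2/1/1 and 26/1/1/1/1 layouts both average 30/5 = 6, yet fixed terms cost about 3 and 6-7 points there if systems do not differ. The average hides single-clinic systems.

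**Conclusion.** The mismatch between the stratified randomization and the primary model is on the page and unexplained. It concerns efficiency, not validity. If systems differ, and the test is calibrated, the standard error for arm is too large and the benefit of stratifying is not realized. Under the assumptions listed, with three to six systems holding 30-50% of between-clinic variance, the planned test runs at about 3-5% instead of 5%, and about 1-5 points of power are given up. No figure can be claimed for this trial itself, because the number of systems and the variation between them are not stated. Confidence is high in the mismatch and in the direction of the standard error; none is claimed for the sign or size of the net effect on power. The point is worth correcting because the change is cheap.

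**What to change.** In section 9.0:

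1. Specify the primary model as arm + health system as randomized + clinic baseline screening rate, with a clinic random intercept, using the baseline rates that section 7.0 already collects.
2. In the same sentence, specify REML-type estimation with a between-clinic degrees-of-freedom correction.
3. State what counts as a health system for the randomization.
4. Set the form of the term from the actual list of systems, known at randomization, before outcomes are seen by arm: fixed effects only if every system has several clinics in both arms; otherwise, with many small or single-clinic systems, a random system effect.

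If the team prefers to leave health system out, the plan should say so and give the reason.

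The cost is SAP wording and a few lines of code. The statistical downside, if systems turn out not to differ, is up to about 2-3 points of power for fixed terms with three to six systems of several clinics each, and about 6-7 points with ten three-clinic systems or several single-clinic ones. The form rule in item 4 is meant to avoid the latter. The random effect avoided this loss in the layouts simulated, at a type I error of up to about 6%.
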